10.4.2. Laboratory Tests

Descriptive summaries of laboratory values, including changes from baseline and treatment-emergent abnormalities, will be generated. Shift tables reflecting changes from baseline (e.g., normal to low, high) will be presented for a subset of laboratory parameters.

The liver function tests, namely ALT, AST, ALP, and TBL, are used to assess possible drug-induced liver toxicity (DILI). A listing of liver function test results that meet DILI criteria will be generated.

10.4.3. 12-Lead Electrocardiogram

The RR, PR, QRS, and QT intervals will be measured and read by a central laboratory. HR will be calculated as $60 / (\text{RR} \times 1000)$ (with RR expressed in msec) and rounded to the nearest integer.

Correction for Heart Rate

Corrected QT interval (QTc) will be calculated using the manually over-read QT values. Each individual ECG QT value will be corrected for HR. The measured QT data will be corrected for HR using QTcF as per the following formulae/method (with QT, RR and QTc expressed in msec):

Fridericia's Correction:

$$QTcF = \frac{QT}{(RR / 1000)^{(1/3)}}$$

ECG Numeric Variables

HR, PR, QRS, and QTcF will be summarized using descriptive statistics. For each time point of measurement, the changes from baseline will be summarized using descriptive statistics.

Categorical Analysis

The incidence count and percentage of patients with any postdose QTcF values of >450 msec, >480 msec, and >500 msec will be tabulated. Patients with QTcF values >520 msec will be listed with corresponding baseline values, Δ QTcF, and baseline and treatment HR. The incidence count and percentage of patients with Δ QTcF increase from baseline of >30 msec and >60 msec will be tabulated.

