8 SAFETY ANALYSES

All safety analyses will be performed on the Safety Analysis Population and will be presented by each treatment group and the combined active treatment. In general safety data will be presented by descriptive statistics only and by nominal visit (if applicable). Safety data collected on unscheduled visits will be presented in listings only.

The treatment emergent period is defined as first dose through the end of study for subjects who complete the full treatment period of 12 weeks. If a subject discontinues study drug early, then the treatment emergent period will be first dose through four weeks after last dose.

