8.3 Safety Laboratory Data

Safety laboratory data and change from baseline will be summarized by treatment group and visit using descriptive statistics.

Laboratory parameters that are graded in CTCAE Version 4.03 will be summarized by CTCAE grade. In the summary of laboratory parameters by CTCAE grade, for parameters with CTCAE grading in both high and low direction (e.g., calcium, glucose, magnesium, potassium, sodium), CTCAE in high and low directions will be summarized separately. Subjects with treatment-emergent laboratory abnormalities of Grade 3 or higher will also be summarized. Shift from baseline to the worst post-baseline CTC grade of Grade 3 or higher will also be presented for select laboratory tests of interest including neutrophils, platelets, hemoglobin, creatine kinase, AST, ALT, total bilirubin, triglycerides, and cholesterol.

Absolute values over time will also be plotted for select laboratory tests of interest including neutrophils, platelets, hemoglobin, creatine kinase, AST, ALT, total bilirubin, triglycerides, and cholesterol. Listings of laboratory values will be generated and the results that are out of the reference range will be flagged.

8.3.1 *Potential Drug-induced Liver Injury*

The liver function tests, namely alanine aminotransferase (ALT), aspartate aminotransferase (AST), alkaline phosphatase (ALP), and total bilirubin (TBL) are used to assess possible drug - induced liver injury (DILI).

A graph of distribution of peak values of ALT versus peak values of TBL will be presented. ALT and TBL values will be presented on a logarithmic scale. The graph will be divided into

4 quadrants with a vertical line corresponding to $3 \times$ the upper limit of normal (ULN) for ALT and a horizontal line corresponding to $2 \times$ ULN for TBL.

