The number and percentage of subjects with elevated liver function tests (based on safety laboratory data) during the TEAE period will be summarized by categories of elevation ($>3 \times$ ULN, $> 5 \times$ ULN, $> 10 \times$ ULN, $> 20 \times$ ULN for ALT and AST, $> 1.5 \times$ ULN for ALP, and $> 1.5 \times$ ULN and $> 2 \times$ ULN for TBL), along with the following categories of normalization (i.e. return to $\leq 1 \times$ ULN, or return to baseline if baseline $>$ ULN): never normalized, normalized after permanent discontinuation of study drug, normalized during treatment period and elevated after permanent discontinuation of study drug. Potential Hy's law cases will be investigated by summarizing the number of subjects with elevated ALT or AST ($> 3 \times$ ULN), elevated ALP ($> 2 \times$ ULN) and elevated total bilirubin ($> 2 \times$ ULN) where transaminase elevation coincides with or precedes BILI elevation.

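### The SAP's potential Hy's law count requires ALP above 2 × ULN, so it leaves out the hepatocellular cases that the label ordinarily describes

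*SAP*

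**What the plan says.** SAP 8.3.1 (Potential Drug-induced Liver Injury) plans three outputs on liver tests.

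- **A graph** of each subject's peak ALT against peak total bilirubin (TBL), divided into "4 quadrants with a vertical line corresponding to $3 \times$ the upper limit of normal (ULN) for ALT" and a horizontal line at 2 × ULN for TBL. It carries no ALP, AST or timing condition.
- **Single-test elevation tables.** ALT and AST are cut at 3, 5, 10 and 20 × ULN, ALP at 1.5 × ULN only, and TBL at 1.5 and 2 × ULN.
- **A potential Hy's law summary.** The sentence opens "Potential Hy's law cases will be investigated by summarizing the number of subjects with elevated ALT or AST ($> 3 \times$ ULN" and continues with "elevated ALP ($> 2 \times$ ULN) and elevated total bilirubin ($> 2 \times$ ULN) where transaminase elevation coincides with or precedes BILI elevation".

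SAP 8.3 adds listings: "Listings of laboratory values will be generated and the results that are out of the reference range will be flagged". SAP 8 states that safety results "will be presented by each treatment group and the combined active treatment". Protocol 10.4.2 promises one further output: "A listing of liver function test results that meet DILI criteria will be generated". The visible text of neither document says what those DILI criteria are, and SAP 8.3.1 does not carry that listing forward by name.

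**The concern.** The Hy's law sentence joins its three laboratory conditions with 'and', so ALP above 2 × ULN is required. In its ordinary meaning a Hy's law case is a transaminase rise with a bilirubin rise in which cholestasis does not explain the bilirubin, that is, without a marked ALP rise. The ALP inequality therefore points the wrong way. A subject with the pattern that matters most for drug-induced liver injury is left out, while a subject with a mixed or cholestatic picture is counted under the Hy's law label.

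Safety and tolerability is a secondary objective, and both documents name ALT, AST, ALP and TBL as the tests for assessing liver injury. This is the only planned table that joins those tests within a subject. A zero in it would naturally be read as the absence of a liver signal.

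**Working it through.** **Is it one joint condition?** The alternative is that ALT/AST, ALP and TBL are to be summarised separately. Three features of SAP 8.3.1 count against that.

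1. The sentence describes a single number of subjects under a single label.
2. Separate single-test counts are already specified in the sentence before it, with a different ALP cut (1.5 × ULN, not 2 × ULN).
3. The closing timing clause relates the transaminase rise to the bilirubin rise within a subject, which has no meaning for separate counts. The clause does not mention ALP, so it links only those two tests; that ALP is required follows from the 'and' and from points 1 and 2.

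**Which patterns does each output select?** Take five yes/no conditions: ALT > 3 ×, AST > 3 ×, TBL > 2 ×, ALP > 2 × ULN, and timing met. There are 2^5 = 32 patterns.

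- SAP rule: (ALT or AST) and TBL and ALP > 2 × and timing = 3 × 1 × 1 × 1 = 3 patterns.
- Ordinary rule: (ALT or AST) and TBL and ALP not > 2 × and timing = 3 × 1 × 1 × 1 = 3 patterns.
- Overlap: 0. This follows by construction, since the rules differ only in the direction of the ALP condition. It shows that the SAP rule captures none of the ordinary cases, not merely fewer of them.
- Graph, upper-right quadrant: ALT and TBL. It contains 2 of the 3 ordinary patterns (ALT only; ALT and AST). The third, AST only, appears in neither joint output.

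Invented profiles, in multiples of ULN, show the effect:

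| Profile | ALT | AST | TBL | ALP | Timing met | SAP count | Ordinary rule | Graph quadrant |
|---|---|---|---|---|---|---|---|---|
| A | 10 | 6 | 3 | 1.2 | yes | no | yes | yes |
| B | 2 | 5 | 2.5 | 1.2 | yes | no | yes | no |
| C | 3.5 | 2 | 3 | 6 | yes | yes | no | yes |
| D | 5 | 4 | 3 | 1 | no (TBL rose first) | no | no | yes |

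Profiles A and C are the core of the problem: the hepatocellular case is missed and the cholestatic one is counted. B shows the AST-only gap in the graph. D shows that the count and the graph also differ on timing.

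**Can the count be recovered elsewhere?** The single-test tables do not join tests within a subject, and their ALP cut of 1.5 × ULN does not give the 2 × ULN split. The listings hold the values, but the reader would have to rebuild the count by hand. The protocol's DILI listing rests on unstated criteria.

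**Size.** The documents give no expected number of liver cases, so the number affected cannot be computed. For illustration, the planned combined active group is 5 × 35 = 175 (SAP 4). Assume 1 to 3 cases meeting the ordinary rule, and no others. Exact (Clopper-Pearson) 95% intervals run from the 2.5% quantile of Beta(x, n − x + 1) to the 97.5% quantile of Beta(x + 1, n − x). For x = 0 the upper limit is 1 − 0.025^(1/n), which for n = 175 is 1 − 0.025^(1/175) = 2.09%.

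| Cases | Count under SAP rule | Count under ordinary rule |
|---|---|---|
| 1 | 0/175 (0 to 2.09%) | 1/175 = 0.57% (0.01 to 3.14%) |
| 2 | 0/175 (0 to 2.09%) | 2/175 = 1.14% (0.14 to 4.07%) |
| 3 | 0/175 (0 to 2.09%) | 3/175 = 1.71% (0.35 to 4.93%) |

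In a single arm of 35, one such case would show as 0/35 (0 to 10.0%) instead of 1/35 (2.86%, 0.07 to 14.92%).

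**The case against.** The strongest objection is that calling the rule wrong depends on a definition that neither document supplies. On the documents alone, one can say only that the count requires raised ALP and the graph does not. This stands in part: the meaning of Hy's law used here is the ordinary sense of the term and should be read as an assumption. But the exclusion of subjects with ALP at or below 2 × ULN follows from the SAP's own words. The mismatch with the graph is internal to one section, and reporting the count irrespective of ALP as well would remove any dependence on a single definition.

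A second objection is that little is lost. Safety is descriptive only, ALT-driven cases show on the graph, and every value is in the listings. The safety monitoring committee reviews the safety data (Protocol 9), so oversight does not hang on this table. Protocol 5.3 also excludes entrants with ALT/AST or bilirubin at or above 2 × ULN or a history of Gilbert's syndrome, so few cases may arise. All of that is fair and limits the severity. It does not make the labelled count right, and with few cases expected, omitting one matters more.

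A third objection is that the case numbers above are invented. They are, and they show only how the table would read. It is also possible that the intended program already uses the opposite ALP condition, in which case only the wording needs correcting.

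**Conclusion.** The concern holds. Followed exactly, SAP 8.3.1 would report a potential Hy's law count that leaves out every subject with ALT or AST > 3 × ULN, TBL > 2 × ULN and ALP ≤ 2 × ULN, and contains only subjects with ALP > 2 × ULN. The exclusion rests on the SAP's wording alone; calling it an error rests also on the ordinary meaning of Hy's law. The number of subjects affected is unknown: it is zero if no case of either kind occurs. Otherwise each hepatocellular case is missed, and each mixed or cholestatic case meeting the rule is counted under the wrong label. The primary efficacy analysis is untouched and the raw data stay visible, so this is a correction that should be made before the SAP is final rather than a threat to the trial.

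**What to change.** In SAP 8.3.1:

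1. Define the potential Hy's law count as ALT or AST > 3 × ULN, with TBL > 2 × ULN at the same time or later, and ALP < 2 × ULN.
2. Report the same count irrespective of ALP beside it. This also captures a subject with ALP of exactly 2 × ULN, whom neither strict inequality takes in.
3. List every subject in the second count with the ALP value. State whether this is the listing promised in Protocol 10.4.2, and write its criteria down.
4. Either put the graph on the same basis (ALT or AST, same timing rule) or footnote that its upper-right quadrant uses peak ALT only, with no timing condition, and so need not match the counts.

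If the sponsor does intend ALP > 2 × ULN as a requirement, the SAP should say why and give that count another name. The cost is SAP wording and one descriptive safety derivation on data already collected, with no new data and no protocol amendment.

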8.4 Vital Signs

Vital signs, including heart rate (HR), systolic blood pressure, and diastolic blood pressure, values and changes from baseline will be summarized by treatment group and visit using descriptive statistics, and listed by subject.

8.5 Other Safety Data

Abnormal physical examination results will be listed by subject and clinical significance.

9 PHARMACOKINETIC ANALYSES

9.1 PK Concentration

ESK-001 and two metabolites' concentration values will be summarized with descriptive statistics by timepoint and treatment group, where available, using the PK analysis population. ESK-001 and metabolite concentration-time plots will also be presented.

Boxplots of PK concentration by treatment and timepoint will also be presented for each analyte.

Population PK analyses will be conducted and summarized in a separate report.

10 PHARMACODYNAMIC ANALYSES

T/B/NK cell counts will be summarized descriptively by treatment group and visit, and subject level data will be presented in a listing.

All other pharmacodynamic PD/biomarker endpoints are outside the scope of this SAP and will not be described and reported in a separate analysis plan and report.

11 INTERIM ANALYSIS

No formal interim analysis is planned for this study. Week 12 analysis is the primary analysis to evaluate the efficacy, and week 16 analysis is the safety follow up analysis. Prior to study database lock, the unblinded Week 12 data and analyses will only be reviewed by a select group of individuals who are not directly involved in the study as documented in the study unblinding list governed by SOP-053 Unblinding Events and Procedures.

Per protocol, routine interim safety monitoring during the trial will be conducted by an independent Safety Monitoring Committee (SMC). Based on review of the safety data, the SMC will make recommendation to continue the trial as is or to make modifications to the trial or stop the trial. Details regarding the membership of the SMC, its conduct, frequency of the review of safety data and the scope of the data review are described in the SMC Charter.

12 SUMMARY OF CHANGES FROM PROTOCOL-DEFINED ANALYSES

APPENDIX A SCHEDULE OF ASSESSMENTS

Procedure	Screening	Treatment Period (Weeks)							ET	Safety Follow-up (Weeks)	
			1	2	4	8	12	US		14	16/EOS
Timing of Visit (Days)	-28 to -1	1	8	15	29	57	84	-	-	98	115
Visit Window (Days)	28 to -1		±1	±1	±3	±3	±3	-	-	±3	±3
Informed consent	X										
Inclusion and exclusion criteria	X	X									
Vital signs	X	X	X	X	X	X	X	X	X	X	X
Physical examination ^A	X	X	X	X	X	X	X	X	X	X	X
Medical history	X	X								X	
Pregnancy test (WOCBP only) ^B	X	X			X	X	X	X	X		X
FSH (postmenopausal women only) ^C	X										
HIV, HBV, HCV screening	X										
QuantiFERON TB test ^D	X										
Coagulation	X										
Complete blood count	X	X		X	X	X	X	X	X		X
Serum chemistry	X	X		X	X	X	X	X	X		X
Fasting lipid panel		X			X						X
Immunoglobulin levels (total)		X ^E			X	X	X				X
12-lead ECG	X	X ^E		X	X	X	X	X	X		X
Urinalysis	X	X			X		X		X		X
DNA sample ^F		X									

Procedure	Screening	Treatment Period (Weeks)							ET	Safety Follow-up (Weeks)	
			1	2	4	8	12	US		14	16/EOS
Timing of Visit (Days)	-28 to -1	1	8	15	29	57	84	-	-	98	115
Visit Window (Days)	28 to -1		±1	±1	±3	±3	±3	-	-	±3	±3
Study drug administration at site ^G		X			X	X	X				
Study drug dispensing ^H		X			X	X					
AE/con-med review	X	X	X	X	X	X	X	X	X	X	X
Disease activity skin assessments ^I	X	X	X	X	X	X	X	X	X	X	X
PRO ^J		X		X	X	X			X		X
PD/biomarkers		X					X				
Skin biopsy and tape stripping ^{F,K}											
Plasma biomarker profile ^L		X ^E		X	X	X	X		X		X
Blood RNA-seq profile ^M		X ^E		X	X	X	X		X		X
Blood cell-based PD biomarkers ^{N,O}		X			X	X	X			X	
T/B/NK counts		X ^E			X	X	X				X
PK blood sampling ^P		X			X	X	X		X ^Q	X	

Footnotes

EOS = end of study; ET = early termination; US = unscheduled visit

- A. Full physical examination at Screening and Day 1; abbreviated physical examination symptom driven at all other visits.
- B. Serum pregnancy test at Screening; urine pregnancy test at other indicated visits.
- C. Menopause is defined as absence of menses for 12 consecutive months.
- D. QuantiFERON TB tests should not be performed within 4 weeks of COVID-19 mRNA vaccinations or boosters. If a patients test result is indeterminate it may be retested one time. If both tests are indeterminate the patient will be considered a screen fail.
- E. Predose
- F. Optional, collected only if patient provides specific consent.

- G. Administration of the visit day dose of study drug by the site staff. Patients should be reminded to bring their study drug with them to the clinic and take their dose when instructed by the site staff. Randomization occurs prior to first administration of study drug on Day 1.
- H. Dispense sufficient study drug to last until the next study visit
- I. Includes PASI, BSA and sPGA
- J. Patient reported outcomes (DLQI, EQ-5D and NRS)
- K. Lesional and nonlesional samples; predose on Day 1
- L. Biomarker panel, exploratory proteomics
- M. Exploratory transcriptomics
- N. To be conducted at selected study sites. Fresh blood needs to be collected and cell assays conducted on the day of collection.
- O. PD Samples for patients will be collected on Day 1 and Week 8 predose and 2 hours (± 15 min) and 4 hours (± 15 min) postdose. At Week 4 and 12 patients will take their dose in the clinic and a PD sample will be collected predose. A random sample will be taken at Week 14.
- P. PK Samples for patients will be collected on Day 1 and Week 8 predose and 30 minutes (± 5 min), 1 hour (± 5 min), 2 hours (± 15 min) and 4 hours (± 15 min) postdose in a fasted condition. Patients may have a snack between the 2- and 4-hour draw. At Week 4 and 12 patients will take their dose in the clinic and a PK sample will be collected predose. A random sample will be taken at Week 14.
- Q. Collected if the ET visit is within 14 weeks of the initiation of study drug treatment.

APPENDIX B ANALYSIS VISITS

The following analysis windows will be used to define the analysis visits for each study assessment type.

Table 2 Analysis Visits for Disease Activity Skin Assessments

Analysis Visit	Target Day	Visit Window (Days)
Baseline	1	Screening – Day 1
Week 1	8	2 – 11
Week 2	15	12 – 21
Week 4	29	22 – 42
Week 8	57	43 – 70
Week 12	85	71 – 91
Week 14	99	92 – 105
Week 16	113	105 – 126

Table 3 Analysis Visits for Patient Reported Outcomes

Analysis Visit	Target Day	Visit Window (Days)
Baseline	1	Screening – Day 1
Week 2	15	2 – 21
Week 4	29	22 – 42
Week 8	57	43 – 70
Week 12	85	71 – 98
Week 16	113	99 – 126

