6.8. Administration of Study Drug

The study site staff will administer a dose of study drug to each patient on Day 1 (first dose), and on the Week 4, 8, and 12 visit days. Patients should be clearly instructed not to take study drug on these study Days, but to bring their study drug with them to the clinic and take [REDACTED]

Study drug will be dispensed to patients as a 4-week supply at the Day 1, Week 4, and Week 8 visits.

At the Week 4, 8 and 12 study visits patients must return all study drug [REDACTED]

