Appendix C Dermatology Life Quality Index (DLQI)

Hospital No: Date:

Name: Score:

Address: Diagnosis:

**The aim of this questionnaire is to measure how much your skin problem has affected your life
OVER THE LAST WEEK. Please tick (✓) one box for each question.**

1. Over the last week, how **itchy, sore, painful or stinging** has your skin been?
Very much
A lot
A little
Not at all
2. Over the last week, how **embarrassed or self conscious** have you been because of your skin?
Very much
A lot
A little
Not at all
3. Over the last week, how much has your skin interfered with you going **shopping** or looking after your **home or garden**?
Very much
A lot
A little
Not at all Not relevant
4. Over the last week, how much has your skin influenced the **clothes** you wear?
Very much
A lot
A little
Not at all Not relevant
5. Over the last week, how much has your skin affected any **social or leisure** activities?
Very much
A lot
A little
Not at all Not relevant
6. Over the last week, how much has your skin made it difficult for you to do any **sport**?
Very much
A lot
A little
Not at all Not relevant
7. Over the last week, has your skin prevented you from **working or studying**?
Yes
No Not relevant

If "No", over the last week how much has your skin been a problem at **work or studying**?
A lot
A little
Not at all
8. Over the last week, how much has your skin created problems with your **partner** or any of your **close friends** or **relatives**?
Very much
A lot
A little
Not at all Not relevant
9. Over the last week, how much has your skin caused any **sexual difficulties**?
Very much
A lot
A little
Not at all Not relevant
10. Over the last week, how much of a problem has the **treatment** for your skin been, for example by making your home messy, or by taking up time?
Very much
A lot
A little
Not at all Not relevant

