5 GENERAL STATISTICAL CONSIDERATIONS

The primary analysis for the efficacy endpoints will be conducted using data collected through the 12-week treatment period. Data will be cleaned and locked prior to conducting the primary analysis.

The final analysis will be conducted after all subjects have completed their Week 16 or end of study (EOS) visit and after all study data is cleaned and locked.

SAS® version 9.4 or higher will be used for statistical analyses, tabulations, and graphical presentations.

In general, descriptive summaries will be presented by treatment groups (placebo and ESK-001 dose levels) and overall, for values at each visit. The descriptive summary for continuous variables will also be provided for the change from baseline and, if appropriate, for the change from week 12 to week 16. Summaries of continuous variables will include the number of subjects (N), mean, standard deviation (SD), median, Q1, Q3, minimum, and maximum. If there are variables with highly skewed distribution (e.g. log-normal distribution), then the geometric mean and %CV will also be reported in descriptive summaries. Inferential analysis for those variables may be performed after log-transformation as deemed appropriate. Descriptive summaries for categorical variables will include the number and percentage of subjects. Unless otherwise stated, denominators for percentages will be the number of subjects in the analysis population.

Between-group comparisons will focus on the comparative performance of a single ESK-001 dose versus placebo. All statistical tests will be conducted at a 2-sided significance level of 0.05. The corresponding p-values and two-sided 95% confidence intervals will be reported.

In general, baseline is defined as the last non-missing value prior to the first dose date and time. For subjects randomized but not dosed, the last non-missing value prior to the randomization date will be used as baseline. For any additional considerations, refer to each specific data section for details.

In general, efficacy data and other non-safety data will be presented by analysis visits as defined by the analysis visit window. Data collected at unscheduled or early termination (ET) visits will also be mapped to analysis visits as defined in [Appendix B](#). If a value does not fall within an analysis window, it will not be included in the summary analysis or comparative analysis.

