However, these values will be included in data listings and SAS data sets. When more than 1 value is available within the same analysis visit, the value collected closest to the target visit day will be used for analysis. If 2 values are equidistant to a target visit day (for example, 1 value is before and the other value is after the target day), then the value from the later date will be used for analysis.

Safety lab, ECG and PK data will be summarized by the nominal visit (per protocol). Unscheduled visits will be presented in listings only.

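### SAP Appendix B's Week 12 target day and its mapping of unscheduled and ET values let an assessment made after the last dose replace, or more materially stand in for, the Week 12 value

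*SAP*

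**What the plan says.** **Windows.** SAP Appendix B, Table 2 (PASI, BSA, sPGA) has "Week 12 85 71 – 91". Table 3 (DLQI, EQ-5D, NRS) has "Week 12 85 71 – 98". Table 2 ends Week 14 on Day 105 and also starts Week 16 on Day 105.

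**Selection rules.** SAP Section 5 states: "Data collected at unscheduled or early termination (ET) visits will also be mapped to analysis visits as defined in" Appendix B. When a window holds several values, "the value collected closest to the target visit day will be used for analysis". If two are equally distant, "then the value from the later date will be used for analysis". The visible text gives scheduled visits no priority and sets no treatment-status condition.

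**Schedule.** Protocol Section 1.3 and SAP Appendix A both place Weeks 12, 14 and 16 on Days 84, 98 and 115, each ±3 days. Skin assessments are made at unscheduled and ET visits. In the protocol schedule, patient-reported outcomes are collected at Week 12, ET and Week 16, but not at unscheduled visits or Week 14.

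**Dosing around Week 12.** Under Protocol Section 6.8 the site gives a dose "on the Week 4, 8, and 12 visit days", and "Study drug will be dispensed to patients as a 4-week supply at the Day 1, Week 4, and Week 8 visits". Nothing is dispensed at Week 12, so that visit's dose is the last. Protocol Section 4.3 puts the skin assessments before it.

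**Early stopping.** Protocol Section 7.2 asks patients who stop drug to stay for all scheduled assessments. Those who will not or cannot do so have an ET visit 2 weeks ±7 days after stopping. SAP Section 7 counts patients who leave the study before Week 12 as non-responders in responder analyses. SAP Section 5.3 imputes nothing else unless the SAP says so.

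**The concern.** The endpoints are defined after 12 weeks of treatment, and the scheduled Week 12 assessment is made before that visit's dose. The SAP's target day is one day after the scheduled day, and its tie rule favours the later value. An extra assessment shortly after the last dose can therefore win over a visit held exactly on time.

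The windows also reach past the end of treatment. An ET value taken one to three weeks off drug can be labelled Week 12 when no scheduled value exists. That affects the ANCOVA endpoints (%BSA, DLQI, PASI change), for which no imputation or treatment-status rule is stated. For PASI-75 and sPGA 0/1 it leaves two rules competing for the same patient.

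**Working it through.** **1. Target days.** Compare 7 × week + 1 with the two sets of days.

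| Week | 7w + 1 | Schedules of assessments | SAP Appendix B |
|---|---|---|---|
| 1, 2, 4, 8 | 8, 15, 29, 57 | 8, 15, 29, 57 | 8, 15, 29, 57 |
| 12 | 85 | 84 | 85 |
| 14 | 99 | 98 | 99 |
| 16 | 113 | 115 | 113 |

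The last three rows disagree. Appendix B follows the formula throughout. The schedules leave it at Week 12, although a 28-day supply from Day 57 does run to Day 84 (57 + 28 − 1).

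**2. Windows.** Cutting at midpoints, with the midpoint day going to the later visit, reproduces the SAP's figures:
- Week 12 starts at (57 + 85)/2 = 71.
- The skin window ends the day before (85 + 99)/2 = 92, so on Day 91.
- The patient-reported window ends the day before (85 + 113)/2 = 99, so on Day 98.
- Week 16 in Table 2 should start at (99 + 113)/2 = 106. Day 105 is 6 days from 99 and 8 from 113, so the overlap is a slip.

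**3. Displacement.** A scheduled Week 12 visit on day v (81 to 87) loses to a later assessment on day x when |x − T| ≤ |v − T|.

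| Visit day v | Later days that win, T = 85 | Later days that win, T = 84 |
|---|---|---|
| 81 | 82–89 | 82–87 |
| 82 | 83–88 | 83–86 |
| 83 | 84–87 | 84–85 |
| 84 | 85, 86 | none |
| 85–87 | none | none |

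For example, |84 − 85| = |86 − 85| = 1 is a tie, so Day 86 is used. Moving the target to Day 84 protects the on-time visit but not the permitted Day 81 visit.

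An ET visit at least 7 days after a last dose given at Week 12 can displace that visit's value in only one case: visit on Day 81 and ET on Day 88 or 89 (distances 3 and 4, against 4). For patient-reported outcomes that is the only scheduled source of displacement.

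**4. Stand-in.** If drug stops on day S, the ET visit falls on S + 7 to S + 21.
- Skin window 71–91: S from 71 − 21 = 50 to 91 − 7 = 84.
- Patient-reported window 71–98: S from 50 to 98 − 7 = 91, capped at 87, the latest in-window Week 12 visit and so the latest last dose.
- With ET exactly 14 days after stopping, S runs from 57 to 77 (skin) and from 57 to 84 (patient-reported).

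A patient who stops on Day 57 and has ET on Day 71 would thus supply a Week 12 %BSA and DLQI after about eight weeks on drug and two weeks off. An ET visit on Day 94 would send PASI to Week 14 and DLQI to Week 12 for the same patient.

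**5. Responder endpoints.** A patient who leaves the study with an ET visit on Days 71 to 91 meets the non-responder rule and also has a windowed Week 12 value. The rule's cut-off, before Week 12, is not tied to a day or a visit, so the visible text does not say which applies.

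**The case against.** Displacement needs an extra skin assessment within days of Week 12. When it replaces an on-time Day 84 visit, the new value is only one or two days after a dose. Nothing in the documents suggests that PASI moves in that time. This stands, and it is why that route is minor.

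A reader might infer that late DLQI scores will commonly pass as Week 12, because the questionnaire looks back one week ("OVER THE LAST WEEK. Please tick") and the window runs to Day 98. The documents do not support that. A patient dosed at the Week 12 visit should have a DLQI from that visit, and a Day 84 score beats a Day 94 score (1 day from target against 9). The case arises only when no closer score exists.

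Nor is Day 98 an error in itself. It is the midpoint limit for an instrument with no Week 14 collection. Starting Week 16 straight after Day 91 would label a Day 92 DLQI as Week 16, although it is 7 days from Day 85 and 21 from Day 113.

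Off-drug Week 12 values are also expected by design, since patients who stop drug are asked to stay. That is fair for scheduled visits. It does not cover an ET value taken as early as Day 71.

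Finally, SAP Section 5 limits the primary efficacy analysis to data from the 12-week treatment period, and non-responder imputation covers much of PASI-75 and sPGA. Both help in part. But the windows extend past that period without saying how the two rules combine, and continuous endpoints have no imputation rule.

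**Conclusion.** The point holds with limited reach. The target days conflict, Day 105 is assigned twice, and the selection rules as written can replace a valid scheduled Week 12 skin assessment with a later one. The number of patients affected cannot be derived from the documents. Displacement should be rare. If it changed one patient's PASI-75 status, that arm's rate would move by 1/35 = 2.9 percentage points. The stand-in route matters more, for %BSA, DLQI and PASI change. For PASI-75 and sPGA 0/1 the defect is an unstated order of precedence.

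A reader might infer three stronger things that the documents do not support:
- That replacement is informative because unscheduled visits follow worsening. Nothing in either document says so.
- That the primary comparison is in danger. The plan assumes 10% against 60% with at least 99% power, so an isolated change of status is unlikely to alter a conclusion.
- That the schedule's days are right and Appendix B's wrong. The documents show only that they differ.

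The conclusion assumes Week 12 visits on Days 81 to 87, a last dose at that visit, and ET 7 to 21 days after stopping. Text directly after the non-responder rule in SAP Section 7 is redacted and could contain a further rule.

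**What to change.** Change the SAP before unblinding:

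- **(a) Section 5.** Use the scheduled-visit value whenever one exists in the window, and an unscheduled or ET value only otherwise. This removes every displacement in step 3, including the Day 81 case that a new target day would not cure.
- **(b) Appendix B.** Reconcile the Week 12, 14 and 16 target days with the schedule of assessments.
- **(c) Table 2.** Start the Week 16 window at Day 106. If (b) changes the targets, recut the windows by the same midpoint convention. With Days 98 and 115, for instance, the midpoint is 106.5 and Week 16 would start on Day 107.
- **(d) Section 7.** State that non-responder imputation takes precedence over a windowed ET value for patients who left the study before their Week 12 visit. State also how off-treatment ET values are handled for continuous endpoints. Item (a) alone leaves this route open.

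The cost is SAP wording and slight extra programming. No new data are needed.
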